8.0 Quality Control and Quality Assurance

The project manager [name] will check over all databases in Qualtrics and generated from tasks for quality assurance monthly. Any missing data or data anomalies will be communicated to the PI for clarification/resolution.

The investigational site will provide direct access to all trial related source data/documents and reports for the purpose of monitoring and auditing by NIMH, and inspection by local and regulatory authorities.

9.0 Data and Safety Monitoring

Digital Data Safety. All surveys and tasks, including those that request information about demographics which could theoretically be used to identify an individual, will be completed digitally and immediately stored on UIC's secure, HIPAA compliant server in a password-protected server that can be accessed only by the PI and her designees (i.e., postdoctoral fellows or project manager affiliated with the study). All additional biological assay data will similarly be stored on UIC's secure server.

With respect to data collected using the BiAffect App, all data will be captured digitally and stored on the HIPAA-compliant server at Sage Bionetworks, where all data from apps in the Apple HealthKit (and associated Android app counterparts) are hosted. As noted in the Protection of Human Subjects section, we will generate an anonymous email address and password to correspond to each study identification number, and this email will serve as the link to match *deidentified participant BiAffect data on the Sage Bionetworks server* with their local study data. Given that this unique email "ID" will be used to identify participants, no PHI will be collected using the BiAffect App, since there are no survey responses that contain PHI.

Similarly, with respect to data collected using the Metricwire App, all data will be captured digitally and stored on the HIPAA-compliant server at Metricwire. As noted in the Protection of Human Subjects section, we will generate an anonymous email address and password to correspond to each study identification number, and this email will serve as the link to match *deidentified participant Metricwire data on the Metricwire server* with their local study data. Given that this unique email "ID" will be used to identify participants, no PHI will be collected using the Metricwire App. Metricwire data will be collected up until July 31st, 2023. After this date, participants will no longer be enrolled into the Metricwire app and no data will be collected.

As noted above, the Oura Ring app will not record any identifying information.

Paper Document Safety. Paper documents containing PHI include those used to register patients in the UIC vendor system to be paid for their participation, which include SSN, address, and name, as well as the SCID-5, which includes date of birth and other demographic information. These documents will be digitized (see notes regarding digital data protections above) and shredded. Any paper documents that have not yet been digitized (e.g., SCID-5 interviews awaiting data entry) will be stored in a locked file drawer in the PI's locked office until they are digitized (see above). Only the PI and the project manager will have keys to this file drawer. Once digitized, all paper documents (except consent forms) will be immediately shredded per UIC protocol for protected health information. Consent forms will be kept in a locked file drawer in the PI's office as per UIC ethics protocol.

Data Monitoring and Report Generation. Each month, the project manager will generate a report from the database, including information about participant flow, demographics, and data completeness. This report will be sent to the PI and all Co-Is for review. Reports will also include detailed (but deidentified) information about any Adverse Events (AEs) (e.g., suicide risk elevation) and follow-up procedures.

Monitoring and Reporting of Mood Changes, Suicide Risk, and Adverse Events. The PI will supervise the clinical postdoctoral fellow as well as the project manager in monitoring changes in suicidal risk and mood symptoms obtained from laboratory visits, daily online surveys, and daily telephone risk screenings. Research staff will be specifically trained to identify significant changes in mood or suicidality in various assessments (see protocol in Protection of Human Subjects section), which will be reported immediately to the PI and further monitored for the duration and impairment criteria described in the Protection of Human Subjects Section (i.e., symptoms must interfere with either relationships or occupational health, and must remain elevated for three days). As described above, participants who experience significant deterioration in mood or who are judged to be at imminent suicide attempt risk will be discontinued from the

protocol and referred for an appropriate level of psychiatric care.

In addition, specific events to be reported to the data safety and monitoring board (DSMB) will be defined by the DSMB at their first meeting prior to the start of the research.

DATA SAFETY AND MONITORING BOARD

Similar to the PI's ongoing clinical trials, the safety of the study will be monitored by a specially-convened Data and Safety Monitoring Board at UIC. This will ensure the independent oversight of issues related to safety/adverse events. The DSMB will monitor the study for AEs, including a significant worsening of symptom severity, imminent suicide risk, substantial functional impairment, and physical effects (e.g., migraine, thromboembolic events). The DSMB will specify the tables and data it wishes to have presented, including moderate to severe side effects and all serious adverse events. DSMB review of this study will occur every six months. At these meetings the DSMB will also review data from participants who have been discontinued or who have dropped out of the study, and reasons for discontinuation. The DSMB will identify if any study procedures should be altered or stopped in the event of an indication of harm to participants attributable to the study interventions. The DSMB will evaluate issues of participant safety as well as the adequacy and integrity of accumulating data, review of enrollment data, and making recommendations regarding safety.

Members of the DSMB:

[name], MPH (CHAIR), Associate Professor and Director of Division of Adolescent Medicine, expertise with hormonal manipulation in vulnerable populations.

[name], LCSW, Social worker at UIC with professional competence in female mental health and suicide risk assessment among diverse populations such as those seen at UIC.

[name], Assistant Professor in Department of Physical Therapy, expertise in clinical research with female populations.

Definitions of Adverse Events

Adverse event means any untoward medical occurrence associated with the use of an intervention in humans, whether or not considered intervention-related.

AE SEVERITY

- **Mild** – Events require minimal or no treatment and do not interfere with the participant's daily activities.
- **Moderate** – Events result in a low level of inconvenience or concern with the therapeutic measures. Moderate events may cause some interference with functioning.
- **Severe** – Events interrupt a participant's usual daily activity and may require systemic drug therapy or other treatment. Severe events are usually potentially life-threatening or incapacitating.
- ***Serious adverse event or serious suspected adverse reaction***. An AE or suspected adverse reaction is considered "serious" if, in the view of either the investigator or sponsor, it results in any of the following outcomes: death, a life-threatening adverse event, inpatient hospitalization or prolongation of existing hospitalization, or a persistent or significant incapacity. Important medical events that may not result in death, be life-threatening, or require hospitalization may be considered serious when, based upon appropriate

medical judgment, they may jeopardize the patient or subject and may require medical intervention to prevent one of the outcomes listed in this definition.

- *Notable examples of serious adverse events in the present study include development of a venous thromboembolism or suicide attempt.

AE STUDY-RELATEDNESS

For all AEs, [name] will urgently collaborate with [name] to determine the AE's causality based on temporal relationship and clinical judgment. The degree of certainty about causality will be graded using the categories below.

Definitely Related – There is clear evidence to suggest a causal relationship, and other possible contributing factors can be ruled out. The clinical event occurs in a plausible time relationship to drug administration and cannot be explained by concurrent disease or other drugs or chemicals. The response to withdrawal of the drug (dechallenge) should be clinically plausible. The event must be pharmacologically or phenomenologically definitive, with use of a satisfactory rechallenge procedure if necessary.

Probably Related – There is evidence to suggest a causal relationship, and the influence of other factors is unlikely. The clinical event occurs within a reasonable time after administration of the drug, is unlikely to be attributed to concurrent disease or other drugs or chemicals, and follows a clinically reasonable response on withdrawal (dechallenge). Rechallenge information is not required to fulfill this definition.

Possibly Related – There is some evidence to suggest a causal relationship (e.g., the event occurred within a reasonable time after administration of the trial medication). However, other factors may have contributed to the event (e.g., the participant's clinical condition, other concomitant events). Although an AE may rate only as "possibly related" soon after discovery, it can be flagged as requiring more information and later be upgraded to "probably related" or "definitely related," as appropriate.

Unlikely to be related – A clinical event whose temporal relationship to drug administration makes a causal relationship improbable (e.g., the event did not occur within a reasonable time after administration of the trial medication) and in which other drugs or chemicals or underlying disease provides plausible explanations (e.g., the participant's clinical condition, other concomitant treatments).

Not Related – The AE is completely independent of study drug administration, and/or evidence exists that the event is definitely related to another etiology. There must be an alternative, definitive etiology documented by [name] or [name].

AE EXPECTEDNESS

[name] will collaborate with [name] to make determinations about whether an AE is expected or unexpected. An AE will be considered unexpected if the nature, severity, or frequency of the event is not consistent with the risk information previously described for the study agent.

10.0 Data Analysis and Statistical Considerations

ANALYTIC STEPS

For each outcome, we will use model fit indices to select the best-fitting hierarchical model before proceeding with analyses. Based on our prior study (K99MH109667) with a similar experimental design and similar data collection structure for daily surveys and lab visits, we expect that the data structure for primary analyses will be observations nested within participants (two-level regression model). In our prior models, inclusion of a third level of nesting (i.e., observations nested within condition nested within individuals) did not improve model fit and did not substantively alter hypothesis tests. Based on the prior study, we also expect that a combination of a random intercept for participant and an autoregressive (day-1) within-person error structure will be included based on model fit.

Testing Experimental Effects: Aim 1 and 2 require that we first evaluate the impact of the experiment on each of the 3 primary suicide outcomes and 9 (RDoC, neurosteroid) mediators described above. Therefore, we will first examine effects of the within-person hormone stabilization experiment on repeated measures outcomes across the menstrual cycle.

1. **For daily outcomes**, we will utilize multilevel models (with 52 days—26 per condition--nested within each individual; two-level models) to predict each repeated measures outcome from covariates (daily pain, illness, PRN medication use) and the interaction between (1) **experimental condition** (a dichotomous variable coded as 0 for natural hormone withdrawal condition and 1 for hormone stabilization condition) and (2) **condition phase**, a categorical (contrast) variable coded as follows: *midluteal baseline phase*, coded as days +1 to +7 after the positive ovulation test, *perimenstrual experimental phase*, coded as days +11 to +17 after the positive ovulation test, and the *medication withdrawal phase*, coded as days +22 to +26 after positive ovulation test (see Figure 6 in grant for study design and timeline). **Number of daily observations per person.** For the primary contrast between the midluteal and perimenstrual experimental phases, there are 28 observations per person—14 per condition (7 midluteal, 7 perimenstrual). Based on our preliminary data from the K99 trial (identical experimental manipulation), we anticipate receiving an average of 24 observations per participant.
2. **For laboratory visit outcomes**, we will again utilize multilevel models (with 10 labs per person—5 per condition—nested within individuals; two-level models). A two-level model will predict each repeated measures lab outcome from covariates (daily pain, illness, PRN medication use) and the interaction between (1) **experimental condition** (a dichotomous variable coded as 0 for natural hormone withdrawal condition and 1 for hormone stabilization condition) and (2) **condition phase**, a categorical (contrast) variable coded as follows: *midluteal baseline visit*, *perimenstrual experimental visit*, and the *medication withdrawal visit*. **Number of lab observations per person.** For the primary contrast between the midluteal and perimenstrual experimental phases, there are 4 observations per person—2 per condition. Based on our preliminary data from the K99 trial (identical experimental manipulation), we anticipate very minimal missing laboratory data (see grant for details) but have estimated that on average each completer participant will miss .25 visits.
3. **Hypothesized Pattern of Effects for Daily and Lab outcomes:** A significant interaction between experimental condition and condition phase is hypothesized for all twelve specified outcomes such that, in the natural withdrawal condition we expect deleterious changes from the midluteal phase to the premenstrual and menstrual phases (due to corresponding hormone withdrawal), but in the hormone stabilization condition we expect no deleterious changes (or less severe changes) from the midluteal to the premenstrual and menstrual phases (since hormone withdrawal is prevented).

Testing Associations Between Mediators and Suicide Outcomes: Aim 1 and 2 next require that we evaluate the day-to-day or week-to-week associations between single mediators (listed above) and suicide outcome variables on the same day or visit. This will be carried out in similar multilevel models as above, predicting each of the three primary suicide outcomes from person-centered values for each of the 9 mediators (listed above).

Testing Interactive Effects of Hopelessness and Arousal on Suicide Outcomes: Interactions among hopelessness and arousal will be examined as predictors of suicide outcomes and as mediators of the experimental effect. In order to test this, we examine day-to-day interactive effects of daily person-centered hopelessness (noted above) and daily person-centered arousal indices (noted above) predicting same-daily suicide outcomes (noted above). We predict that higher-than-usual hopelessness on a given day will predict greater same-day risk on suicide outcomes, but only when arousal is *also* higher than usual for that individual.

4. Evaluating Mediation Where Appropriate. Finally, each aim indicates that **mediation** will be explored as appropriate. Only when analyses indicate significant effects of the experiment on both the suicide outcome and any mediator, as well as significant associations between the person-centered variable (or interaction variable) and the suicide outcome, we will utilize methods provided by **Bauer, Preacher, and Gil (2006)** to construct a confidence interval for the level 1 indirect effect of experimental condition (condition X phase) on the suicide outcome via the mediator.

Testing for normative cyclical change in the HC group. Aim 3 seeks to characterize how gene expression for GABA_{AR} subunits varies across pre-specified menstrual cycle phase in response to hormonal change. In N=40 HC participants, we will run multilevel growth models to predict subunit gene expression (one model per gene) from specific cycle phase. We will test all pairwise comparisons between midluteal, perimenstrual, and midfollicular phases, controlling for ALLO level, to capture high P4 and ALLO states (midluteal), P4 and ALLO withdrawal (perimenstrual), and low P4 and ALLO (midfollicular).

Testing for group differences between participants with past-month SI and HC. We hypothesize that clinical group moderates the effect of cycle phase on GABA_{AR} composition, such that the primary experimental group shows higher slope of midluteal-to-perimenstrual change in $\alpha 4$ and δ subunits, and lower $\gamma 2$ subunit replacement of δ subunit expression than the HC group. In one model of N=80 total participants, we will test the interaction of group and cycle phase on gene expression outcomes. We also hypothesize a correlation with symptoms, such that increases in $\alpha 4$ and δ subunit expression will be associated with increases in individuals with perimenstrual increases in SI. We also predict that even in the HC group, higher-than-average $\alpha 4$ or δ subunit expression will be associated with higher-than-average negative affect (e.g., depressed mood, anxiety, irritability, or perceived stress). We predict that higher $\gamma 2$ expression will be associated with lower negative affect and perceived stress. We will calculate a person-mean for each subunit's expression (mean level across 5 visits) and a deviation score at each visit (visit level minus person mean). We will test overall correlations (e.g., do participants with higher mean $\alpha 4$ expression have higher negative affect?) and interaction with cycle phase (e.g., does a perimenstrual increase in $\alpha 4$ expression *compared to person-mean* correlate with an increase in negative affect?). To further refine hypotheses, we will generate credible intervals using Bayesian methods in the context of multilevel modeling.

POWER ANALYSIS

80 completers achieves 80% power to detect conventionally small-to-medium sized effects that, in our estimation, are clinically meaningful (i.e., $f^2 = .10$, which would mean that the interaction of condition and phase had uniquely accounted for 10% of the variance in the outcome in the perimenstrual window; Selya et al., 2012, “*A Practical Guide to Calculating Cohen’s f^2 , a Measure of Local Effect Size*”). We posit that if hormone withdrawal (vs. experimental stabilization) does not account for at least 10% of the variance in the outcome during this critical risky window of the menstrual cycle, then this line of research, which involves significant participant burden, is not worth pursuing further.

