For each outcome, we will use model fit indices to select the best-fitting hierarchical model before proceeding with analyses. Based on our prior study (K99MH109667) with an similar experimental design and similar data collection structure for daily surveys and lab visits, we expect that the data structure for primary analyses will be observations nested within participants (two-level regression model). In our prior models, inclusion of a third level of nesting (i.e., observations nested within condition nested within individuals) did not improve model fit and did not substantively alter hypothesis tests. Based on the prior study, we also expect that a combination of a random intercept for participant and an autoregressive (day-1) within-person error structure will be included based on model fit.

Testing Experimental Effects: Both of our two aims require that we first evaluate the impact of the experiment on each of the 3 primary suicide outcomes and 9 (RDoC, neurosteroid) mediators described above. Therefore, we will first examine effects of the within-person hormone stabilization experiment on repeated measures outcomes across the menstrual cycle.

- a. For daily outcomes, we will utilize multilevel models (with 52 days—26 per condition-nested within each individual; two-level models) to predict each repeated measures outcome from covariates (daily pain, illness, PRN medication use) and the interaction between (1) experimental condition (a dichotomous variable coded as 0 for natural hormone withdrawal condition and 1 for hormone stabilization condition) and (2) condition phase, a categorical (contrast) variable coded as follows: *midluteal baseline phase*, coded as days +1 to +7 after the positive ovulation test, *perimenstrual experimental phase*, coded as days +11 to +17 after the positive ovulation test, and the *medication withdrawal phase*, coded as days +22 to +26 after positive ovulation test (see Figure 6 in grant for study design and timeline). Number of daily observations per person. For the primary contrast between the midluteal and perimenstrual experimental phases, there are 28 observations per person—14 per condition (7 midluteal, 7 perimenstrual). Based on our preliminary data from the K99 trial (identical experimental manipulation), we anticipate receiving an average of 24 observations per participant.

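### For the continuous outcomes, a common pre-dose baseline would cut the variance of the condition × phase contrast to about .50–.85 of the planned test's: a cheap gain in efficiency, not the repair of a bias

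*Protocol*

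**What the plan says.** Protocol section 10.0 (Analytic Steps, items 1 to 3) and the SAP (Analytic Steps, a to c) predict every outcome from covariates and the interaction of condition with phase. Condition is "a dichotomous variable coded as 0 for natural hormone withdrawal condition and 1 for hormone stabilization condition". For daily outcomes the midluteal baseline is "coded as days +1 to +7 after the positive ovulation test" and the perimenstrual phase is "coded as days +11 to +17 after the positive ovulation test", seven days each per condition. For lab outcomes "there are 4 observations per person—2 per condition", that is, one visit per phase. The hypothesis is stated once for everything: "A significant interaction between experimental condition and condition phase is hypothesized for all twelve specified outcomes".

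The expected covariance is a participant random intercept with AR(1) errors. On a condition-within-person level, the prior trial is reported as follows: "inclusion of a third level of nesting (i.e., observations nested within condition nested within individuals) did not improve model fit".

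Protocol section 6.0 randomises the order of conditions, puts a washout cycle between them, and starts patch and pill at the day +7 visit. The SAP power section considers one coefficient in a model with 3 predictors, one-tailed, alpha .004.

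Neither document writes out the model equation, sets the baseline condition effect to zero, or adjusts for baseline in another way.

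**The concern.** Three predictors fit condition, phase and their product. With that coding the tested coefficient is a difference of two changes, (perimenstrual minus baseline) on active less the same on placebo, and it uses four cell means. The two baseline means come from untreated days in randomised order, so without carryover their expected difference is known to be zero. Subtracting an estimate of it helps only if a condition's baseline mean predicts its own perimenstrual mean beyond what the person intercept already explains.

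What is at stake is precision. Suicidal ideation is the limiting outcome, with stated power of .81. Mediation is examined only where the experimental effects on both the suicide outcome and the mediator are significant, so lost power there carries forward.

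**Working it through.** **1. The plan's own figure.** Inputs from the SAP: 85 completers, ICC .64, f² = .10, one-sided alpha .004. From both documents: "we anticipate receiving an average of 24 observations per participant".
Effective N = 85 × 24 / (1 + 23 × .64) = 2040 / 15.72 = 129.8 (stated 130). Power from the noncentral t, with noncentrality √(.10 × 129.8) = 3.60, is .816 (stated .81). The figure reproduces. Because f² is defined on the interaction itself, the choice of baseline does not make it wrong.

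**2. Closed form.** Within a person, let s be the residual variance of a seven-day window mean, τ² the person-by-condition variance, and ρ = τ²/(τ² + s) the correlation of baseline and perimenstrual means within a condition, given the person.
- Planned contrast (free baseline effect): variance 4s per person. The τ² component cancels.
- Common baseline: variance 2s(1 + ρ).
- Ratio, common to planned: (1 + ρ)/2.

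With independent residuals of variance 1 and 7 days, s = 1/7, so the planned variance is 4/7 = .571. With ρ = 0 the common-baseline variance is 2/7 = .286, a ratio of .50. With 6 observations received per cell (24/4), both variances rise and the ratio is still .50. The ratio does not depend on the number of completers.

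**3. Autocorrelation, no person-by-condition variance.** Exact GLS for both orders with a period term gives .50 at AR 0 and .3, and .51 at .5. A separate GLS run gives planned-to-common ratios of 1.90 at AR .6 and 1.58 at AR .8, that is .53 and .63.

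**4. Person-by-condition variance (assumed; the documents give none).** At AR .3, s = [7 + 2(6×.3 + 5×.3² + 4×.3³ + 3×.3⁴ + 2×.3⁵ + .3⁶)]/49 = .240. Power is Φ((2.652 + .842)/√ratio − 2.652), which starts from 80% at one-sided .004 and holds the raw effect fixed.

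| τ² as share of residual variance | ρ | (1+ρ)/2 | GLS ratio | Power |
|---|---|---|---|---|
| 0 | 0 | .50 | .50 | .99 |
| 5% | .17 | .59 | .588 | .97 |
| 10% | .29 | .65 | .649 | .95 |
| 20% | .45 | .73 | .73 | .92 |
| 50% | .68 | .84 | .84 | .88 |

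**5. Treatment effects that vary between people.** A slope variance of .25 of the residual variance adds to both variances. At AR .3 and τ² 5%: (.555 + .25)/(.944 + .25) = .67. At AR 0 and τ² 20%: (.452 + .25)/(.571 + .25) = .86, with power .87.

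**6. Lab contrast, one visit per phase.** Here s is the single-visit residual variance. The ratio is .50 with τ² = 0 and rises to .75 (power .92) when τ² equals the residual variance (ρ = .5).

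**7. Carryover.** Let active treatment in order A leave an effect λ in period 2.
- If it lasts through the whole period, the planned interaction is unbiased and the common-baseline estimate is off by −(λ/2)(1 − ρ): −.50λ at ρ = 0, −.41λ at 5% and −.35λ at 10% (AR .3).
- If it touches the baseline days only, the planned interaction is off by .50λ and the common-baseline estimate by ρλ/2, about 0 to .15λ over the same range.

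**8. Day +7.** The patch goes on at the morning visit, the pill is taken at 7 pm, and the survey is completed that evening. Days +1 to +6 are untreated. Protocol section 6.0 lists the visit's tasks, blood draw and self-reports before the patch application. Dropping the day +7 survey costs the common-baseline estimate nothing at ρ = 0, where its variance stays 2/7.

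**The case against.** The planned interaction is a legitimate choice. It is unbiased under the same assumptions, directly tests the stated hypothesis about change from the midluteal phase, cancels any person-by-condition component, and resists carryover that lasts through period 2. All of that stands, and it is why this is an improvement and not a correction. The carryover argument does not settle the choice, because baseline-only carryover reverses it.

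Three stronger readings might be inferred, and the documents do not support them.
- *All twelve tests lose half their information.* Suicidal planning and attempt are dichotomous and come from the daily phone screen. Protocol section 6.0 places calls on medication days and the 4 days after, so days +1 to +6 have none. A linear calculation with 7 + 7 days does not describe these outcomes. Two of the other ten, RSA withdrawal and PEP shortening, rest on lab recording that section 6.0 says was replaced by the Oura Ring.
- *The prior trial shows that a condition's baseline carries no information.* The documents say only that a third level did not improve fit in that trial's models. Prior-trial ICCs are cited for five outcomes, three of them continuous (ideation, hopelessness, agitation). For the others the near-zero premise is extrapolated, so .50 is the favourable end.
- *The stated power is wrong, or will rise to 99%.* Step 1 shows that it reproduces. The gain is a translation at a fixed raw effect that the documents do not give.

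It is also fair to say that the free baseline effect is inferred: the main effects are never listed.

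**Conclusion.** The point holds as a cheap gain in efficiency for the continuous daily and lab outcomes. Under the plan's own expected covariance the planned contrast has about twice the variance it needs. Allowing for what the documents leave open, the common-baseline variance is about .50–.85 of the planned one for daily outcomes and .50–.75 for lab outcomes, so 80% power becomes about 87–99%. This range is a judgement, not a bound: larger person-by-condition variance moves the ratio towards 1, although (1 + ρ)/2 stays below 1.

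The conclusion rests on randomised order, no carryover into the pre-dose days after the washout cycle, the standard reading of the interaction model, and one visit per phase for the lab contrast. The estimand is the same in both analyses.

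**What to change.** In Protocol section 10.0 (Analytic Steps, items 1 and 2) and SAP Analytic Steps a and b, for the continuous outcomes:
- Write out the model. Set the condition effect to zero on pre-dose observations (days +1 to +6 and the day +7 visit measures taken before the patch). Estimate only condition × perimenstrual and condition × withdrawal.
- Drop the day +7 evening survey from the baseline window, because the patch is already on.
- Include a period term and a person-by-condition random intercept, whatever the fit indices say. The planned interaction cancels that component and the constrained estimate does not, so leaving it out could make the standard error too small.
- Keep the planned unconstrained interaction as a sensitivity analysis, and report the pre-dose condition difference as a carryover check.
- State how the phase contrast is formed for the binary planning and attempt outcomes, which this change does not cover.

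The cost is a modest SAP amendment before unblinding, with no new data, visits or participants. The downside to name in the text is that carryover through the whole second period would bias the constrained estimate by up to half the carryover.
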